2. INTRODUCTION

Gepotidacin (GSK21409144) is a novel, bactericidal, first-in-class triazaacenaphthylene antibiotic that inhibits bacterial DNA replication by a distinct mechanism of action and binding site [Bax, 2010; Gibson, 2019] and provides well-balanced inhibition of 2 different type II topoisomerase enzymes [Oviatt, 2022]. This provides activity against most strains of target uUTI uropathogens, such as *Escherichia coli* and *Staphylococcus saprophyticus*, including isolates resistant to current antibiotics [Biedenbach, 2016; Mushtaq, 2019]. Due to well-balanced binding at both enzymes, mutations in both enzymes are needed to significantly affect gepotidacin susceptibility [Oviatt, 2022].

uUTIs, also referred to as acute cystitis, are defined as UTIs in nonpregnant female patients with no known urological abnormalities or complicating comorbidities and not accompanied by signs or symptoms suggesting systemic (i.e., not localized to the bladder) infection, such as fever or costovertebral angle pain [Gupta, 2011; DHHS, 2019]. Common symptoms of uUTIs are pain on urination (dysuria), frequent urination (frequency), sudden onset of the need to urinate (urgency), pain in the lower abdomen (suprapubic pain), inability to start the urine stream (hesitancy), and cloudy urine or blood in the urine (hematuria). In addition to the physical symptoms, uUTIs have been shown to affect a patient's quality of life and their emotional and mental health [Grigoryan, 2022].

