5. STUDY POPULATION

Prospective approval of protocol deviations to recruitment and enrollment criteria, also known as protocol waivers or exemptions, is not permitted.

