7. The participant has a serious underlying disease that could be imminently life-threatening, or the participant is unlikely to survive for the duration of the study period.

Urinary tract infection/renal/urogenital exclusions

8. The participant has uUTI that is known or suspected to be due to fungal, parasitic, or viral pathogens; or known or suspected to be due to *Pseudomonas aeruginosa* or Enterobacteriales (other than *E. coli*) as the contributing pathogen.
9. The participant has symptoms known or suspected to be caused by another disease process, such as overactive bladder, chronic incontinence, or chronic interstitial cystitis, that may interfere with the clinical efficacy assessments or preclude complete resolution of uUTI symptoms.
10. The participant has an anatomical or physiological anomaly that predisposes the participant to UTIs or may be a source of persistent bacterial colonization, including calculi, obstruction or stricture of the urinary tract, primary renal disease (e.g., polycystic renal disease), or neurogenic bladder, or the participant has a history of anatomical or functional abnormalities of the urinary tract (e.g., chronic vesico-ureteral reflux, detrusor insufficiency).
11. The participant has an indwelling catheter, nephrostomy, ureter stent, or other foreign material in the urinary tract.
12. The participant, in the opinion of the investigator, has an otherwise complicated UTI, an active upper UTI (e.g., pyelonephritis, urosepsis), signs and symptom onset ≥ 96 hours before study entry, or a temperature $\geq 101.4^{\circ}\text{F}$ ($\geq 38^{\circ}\text{C}$), flank pain, chills, or any other manifestations suggestive of upper UTI.
13. The participant has known anuria, oliguria, or significant impairment of renal function (creatinine clearance <30 mL/min or clinically significant elevated serum creatinine as determined by the investigator).
14. The participant presents with vaginal discharge at Baseline (e.g., suspected sexually transmitted disease).

Cardiac exclusions

15. The participant has congenital long QT syndrome or known prolongation of the QTc interval.
16. The participant has uncompensated heart failure.
17. The participant has severe left ventricular hypertrophy.
18. The participant has a family history of QT prolongation or sudden death.
19. The participant has a recent history of vasovagal syncope or episodes of symptomatic bradycardia or brady arrhythmia within the last 12 months.

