8.3.2. Vital signs

- Vital signs will be measured at the Baseline Visit (Section 1.3).
- Temperature, systolic and diastolic blood pressure, respiratory rate, and pulse rate will be recorded (before blood collection for laboratory tests).
- Vital signs will be measured in a semi-supine position after 5 minutes of rest.
- If an additional vital sign measurements are obtained (i.e., Scheduled/Unscheduled Visit), clinically significant changes from Baseline will be reported as AEs.

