#### **4.1.2. Baseline Definition**

For all endpoints the baseline value will be the latest pre-dose assessment with a non-missing value, including those from unscheduled visits. If a participant is in the ITT but hasn't taken a dose, they will be included in study population summaries on ITT set.

However, their change from baseline in CSS and **CCI** values will not be included in all the efficacy summary tables based on the CE sets. If time is not collected, Day 1 assessments are assumed to be taken prior to first dose and used as baseline.

If any participant is enrolled with a baseline CSS score < 2, it will be flagged as a protocol deviation and such participants will be excluded from the ITT and all CE analysis sets. If they have taken the dose, then they will be included in the safety analysis set.

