#### 4.5.4.2. Vital Signs

The analyses of vital signs parameters will be based on GSK Core Data Standards.

The following vital signs measurements will be reported before blood collection for laboratory tests for the study at baseline.

- Temperature
- Systolic and Diastolic blood pressure
- Respiratory rate
- Pulse rate

Descriptive statistics (n, mean, standard deviation (SD), median, minimum value (min), and maximum value (max)) will be presented for quantitative measurements of vital signs parameters at baseline and worst-case post-baseline assessments from unscheduled visits (only if there are at least **10** participants with data at unscheduled visits) Participants listing for vital signs parameters will be presented.

Details of the planned displays for vital signs parameters are provided in Output programming specifications (OPS) and will be based on GSK Data Standards and statistical principles.

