### 6.1.3 Protocol Deviations

Important protocol deviations will be summarized.

Protocol deviations will be tracked by the study team throughout the conduct of the study in accordance with the Protocol Deviation Management Plan, entitled Study Deviation Tool and Rules. These protocol deviations will be reviewed to identify those considered as important as follows:

Data will be reviewed prior to freezing the database to ensure all important deviations, which may lead to exclusion of a participant from the analysis sets are captured and categorised in the protocol deviations dataset.

This dataset will be the basis for the summaries of important protocol deviations.

A separate participant listing of all inclusion/exclusion criteria deviations will also be provided. This listing will be based on data as recorded on the inclusion/exclusion page of the eCRF.

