### 6.3.1.2 Vital Signs

Vital Sign Parameter (Absolute)	Units	Potential Clinically Important Range	
		Lower	Upper
Systolic Blood Pressure	mmHg	<85	>160
Diastolic Blood Pressure	mmHg	<45	>100
Pulse Rate	bpm	<40	>110
Temperature	C	$\leq 35$	$\geq 38$
Respiratory Rate	bpm	<10	>20

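### Exclusion criterion 12 prints one fever limit in two units that disagree: 101.4°F is 38.56°C, while 38°C is 100.4°F

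*Protocol*

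**What the plan says.** Criterion 12 in Protocol section 5.2 is meant to keep complicated and upper urinary tract infection out of the study. Among its elements is "a temperature $\geq 101.4^{\circ}\text{F}$ ($\geq 38^{\circ}\text{C}$), flank pain, chills". The Celsius value stands in parentheses directly after the Fahrenheit value, so it reads as the same limit in another unit. The criterion rests on the investigator's judgment and closes with a general reference to other signs of upper infection.

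Other places bear on the point:

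- Protocol section 2 describes uncomplicated infection as "not accompanied by signs or symptoms suggesting systemic (i.e., not localized to the bladder) infection, such as fever" or costovertebral angle pain. It gives no temperature.
- Protocol section 5 says that prospective approval of deviations from enrollment criteria, "also known as protocol waivers or exemptions, is not permitted".
- Protocol section 8.3.2 covers the Baseline measurement: "Temperature, systolic and diastolic blood pressure, respiratory rate, and pulse rate will be recorded". It states no unit for temperature.
- SAP section 6.3.1.2 lists 38°C and above as the upper range of potential clinical importance for temperature. This is a reporting range, not an eligibility rule.
- SAP section 6.1.3 plans a deviation check: "Data will be reviewed prior to freezing the database to ensure all important deviations" are captured, including those that may remove a participant from an analysis set.

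**The concern.** A site has to apply criterion 12 as printed, because no waiver is available. If the two figures are different temperatures, two sites can measure the same value, each follow the protocol, and reach opposite results on the temperature element. One site reads the Fahrenheit figure and the other reads the Celsius figure.

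The element helps to draw the line between uncomplicated and upper infection, which is the boundary of the target population. The later deviation review inherits the problem, because it would have no single threshold for judging a participant who lies between the limits. The planned listing of inclusion and exclusion deviations may not reveal such a participant either. SAP section 6.1.3 bases that listing on what the site entered on the eligibility page of the case report form, and a site that used the Fahrenheit figure would have entered no deviation.

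**Working it through.** **Inputs.** Both come from Protocol section 5.2, criterion 12: 101.4°F and 38°C.

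**Plan's own figure.** The plan presents 101.4°F and 38°C as equal. This does not reproduce in either direction.

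1. Fahrenheit to Celsius, °C = (°F − 32) × 5/9: (101.4 − 32) × 5/9 = 69.4 × 5/9 = 38.56°C, not 38°C.
2. Celsius to Fahrenheit, °F = °C × 9/5 + 32: 38 × 9/5 + 32 = 68.4 + 32 = 100.4°F, not 101.4°F.
3. Gap between the printed limits: 101.4 − 100.4 = 1.0°F, or 38.56 − 38.00 = 0.56°C.

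**Could rounding explain it?** Values that round to 38°C at whole degrees run from 37.5°C to below 38.5°C.

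- Lower end: 37.5 × 9/5 + 32 = 99.5°F.
- Upper end: 38.5 × 9/5 + 32 = 101.3°F.

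101.4°F lies above that range. It rounds to 39°C at whole degrees and to 38.6°C at one decimal. Only dropping the decimals of 38.56 altogether would leave 38, and the printed Celsius limit would then still be a different and lower temperature than the Fahrenheit one.

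**What the temperature element gives for a baseline reading**

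| Reading | Celsius figure (≥38°C) | Fahrenheit figure (≥101.4°F) |
|---|---|---|
| below 100.4°F (below 38.0°C) | does not exclude | does not exclude |
| 100.4°F to below 101.4°F (38.0 to below 38.56°C) | excludes | does not exclude |
| 101.4°F and above (38.56°C and above) | excludes | excludes |

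**Does another place settle it?** No. Criterion 12 holds the only numerical fever limit for eligibility. Section 2 of the protocol has no number, and the 38°C in SAP section 6.3.1.2 serves reporting only.

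**Does it reach the analysis?** Not on the visible text. ITT is defined by enrollment and the primary evaluable set by doses taken (Protocol section 9.2, SAP section 3). The eligibility failure that SAP section 4.1.2 names as removing a participant from these sets is a low symptom score: "If any participant is enrolled with a baseline CSS score < 2, it will be flagged as a protocol deviation". Temperature is not named there.

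**The case against.** The arithmetic is not in dispute. The case on the other side is that the point is small and less certain than it looks.

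- **No planned calculation uses the limit.** This is correct. The primary analysis, the definitions of the analysis sets and the sample size do not depend on it, and the number of participants affected may be zero. It is still a decision rule that sites must apply without waivers, so it is more than a slip in background text.
- **Only the temperature element conflicts, not the whole criterion.** This stands. An investigator who sees a reading in the band as pointing to upper infection, or who finds flank pain or chills, can exclude the participant under either figure. What remains is the participant in the band with no other such sign.
- **Sites can ask.** Protocol section 10.4 describes an inquiry route with medical monitor review. This helps a site that notices the mismatch. It does not help a site that reads only the unit on its own thermometer.
- **The whole point rests on one digit that appears once, in text read from PDF by a program.** This is a fair caution and the reason why checking the source comes first. The conversion itself is certain.
- **An amendment may come too late.** The documents do not say whether enrollment is still open, and SAP Amendment 1 is dated 02 Apr 2025. If enrollment has closed, an amendment changes no eligibility decision, but the check of recorded temperatures keeps its value.

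**Conclusion.** The concern holds. As printed, criterion 12 contains two different fever limits that are 1.0°F (0.56°C) apart, and nothing in the protocol or SAP says which one governs. The effect is confined to the temperature element and to baseline readings from 100.4°F to below 101.4°F. The documents give no count of participants in that band, and no effect on the primary result or on membership of an analysis set is shown.

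This should be fixed because it is a certain contradiction in an eligibility rule that cannot be waived, and the correction is cheap. The conclusion assumes that the supplied text shows the figure as it stands in the sponsor's document. It takes no position on which temperature was intended.

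**What to change.** 1. **Check the source.** Compare the printed figure with the sponsor's protocol document.
2. **Reconcile.** If the figure stands, the sponsor should settle on one threshold and print its exact equivalent in the other unit. No threshold is proposed here. The correction goes through the amendment route, with the IRB and health authority approvals in Protocol section 10.9.1. It alters eligibility decisions only if enrollment is still open.
3. **Check enrolled participants before database freeze.** Identify those with a recorded baseline temperature between the two limits and classify them consistently in the deviation review of SAP section 6.1.3. Work from the recorded temperatures, not only from the deviations that sites reported. Every reading in the band also meets the 38°C reporting limit in SAP section 6.3.1.2, so that limit can serve as the first filter.

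The cost is one corrected figure with its approvals and one look at data already collected. SAP section 4.5.4.2 already plans the output: "Participants listing for vital signs parameters will be presented". No new data are needed, and the definitions of the analysis sets, the primary analysis and the sample size stay as they are.

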2.3.1. Risk assessment

Potential Risk of Clinical Significance	Summary of Data/Rationale for Risk	Mitigation Strategy
Gepotidacin (GSK2140944)		

Cardiovascular Effects
 
Based on nonclinical data, cardiovascular effects were reversible increases in heart rate and blood pressure (dog and monkey); a reversible 10 to 21 msec (4% to 9%) increase in QTc (monkey); and at the highest dose, a reversible 2 to 3 msec (6% to 8%) increase in QRS (monkey).
 
Based on a thorough QTc clinical study, gepotidacin may cause mild, reversible heart rate effects and QT prolongation.
	
In a thorough QTc study, infusion of gepotidacin at doses of 1000 and 1800 mg over 2 h caused a mild increased heart rate effect of approximately 6 to 10 bpm and QT prolongation measured as $\Delta\Delta QTcF$ of 12 to 22 msec. The QT prolongation evolved during the infusion and was quickly reversed over 2 h after the end of the infusion (see Section 5.2.6 and Section 6 of the IB).
 
In Phase 1 and 2 studies, concentration-dependent QT prolongation has been observed during clinical trials with gepotidacin; however, this increase has not translated into medically significant QTc values or changes from Baseline ($QTcF >500$ msec or change from Baseline >60 msec) or cardiovascular safety concerns.
 
In Phase 1 and 2 studies, gepotidacin did not have a clinically relevant effect on cardiac conduction (PR and QRS intervals).
	
See Section 5.2 for excluded cardiac conditions. Close monitoring of clinical parameters and AEs (Section 1.3) will be conducted, and treatment monitoring and evaluation criteria (Section 7.1.2) will be utilized to mitigate cardiovascular effects.
 
Participants taking medications known to increase QT or potent CYP3A4 inhibitors will be excluded (see Section 6.9.2).
 
See also the Renal and Hepatic sections in this table below.

Potential Risk of Clinical Significance	Summary of Data/Rationale for Risk	Mitigation Strategy

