2.3.3. Overall benefit-risk conclusion

Antimicrobial resistance among uropathogens causing uUTI has increased in the past decades [Gupta, 2011; Sanchez, 2016]. However, even in the face of increasing drug resistance to existing agents, few new antibiotics with novel mechanisms of action are being developed. Gepotidacin selectively inhibits bacterial DNA replication by a means that are not utilized by any currently approved human therapeutic agent.

Two Phase 3 clinical studies (Study 204989 [[NCT04020341](#)] and Study 212390 [[NCT04187144](#)]) that assessed gepotidacin (1500 mg BID for 5 days) compared with nitrofurantoin (100 mg BID for 5 days) in uUTI recently stopped early after an interim analysis showed noninferiority in the primary efficacy endpoint of therapeutic response with no safety concerns identified by the Independent Data Monitoring Committee. In the Phase 3 studies, no new safety or tolerability concerns were identified from AEs. Very few SAEs were observed in the Phase 3 studies. There was a higher frequency of gastrointestinal AEs in the gepotidacin arm compared with the nitrofurantoin arm, which was expected based on the Phase 1/2 gepotidacin data and nitrofurantoin label; diarrhea was the most common AE overall and the most common gastrointestinal AE in the gepotidacin arm compared with the nitrofurantoin arm, and the AEs were generally mild to moderate and self-limited.

None of the risks seen to date in participants dosed with gepotidacin preclude further clinical development or submission for regulatory approval. Mitigation strategies have been implemented to promptly identify and appropriately address risks in order to protect participant safety and to better characterize the safety profile of the study intervention (Section 2.3.1). Furthermore, a GSK SRT will monitor safety data instream (see Appendix Section 10.9.6). Careful safety monitoring will also identify any emerging safety issues for gepotidacin and contribute to the benefit-risk profile of gepotidacin.

The investigator may also, at their discretion, discontinue a participant from study intervention at any time and initiate appropriate alternative therapy.

Taking into account the measures taken to minimize risk to participants participating in this study, the potential risks identified in association with gepotidacin are justified by the anticipated benefits that may be afforded to participants with uUTI.

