20. The participant is taking QT-prolonging drugs or drugs known to increase the risk of TdP per the www.crediblemeds.org. “Known Risk of TdP” category at the time of her Baseline Visit, which cannot be safely discontinued from the Baseline Visit (Day 1) through 7 days after the first dose of study intervention; or the participant is taking a strong CYP3A4 inhibitor or a strong P-gp inhibitor.

Cardiac electrocardiogram exclusions

21. The participant has a mean triplicate QTc >450 msec or a mean triplicate QTc >480 msec for participants with bundle-branch block.

Note:

- The QTc is the QT interval corrected for heart rate according to QTcB, QTcF formula, and/or another method. It is either machine read or manually overread.
- The specific formula used to determine eligibility and discontinuation for an individual participant is to be determined prior to initiation of the study. In other words, several different formulas cannot be used to calculate the QTc for an individual participant and then the lowest QTc value used to include or discontinue the participant from the trial.

22. The participant has a documented or recent history of uncorrected hypokalemia within the past 3 months.

Hepatic exclusions

23. The participant has a known ALT value $>2 \times$ ULN.
24. The participant has a known bilirubin value $>1.5 \times$ ULN (isolated bilirubin $>1.5 \times$ ULN is acceptable if bilirubin is fractionated and direct bilirubin $<35\%$).
25. The participant has a current or chronic history of liver disease or known hepatic or biliary abnormalities (with the exception of Gilbert's syndrome or asymptomatic gallstones), including symptomatic viral hepatitis or moderate-to-severe liver insufficiency (Child Pugh class B or C).

Note: Participants with asymptomatic viral hepatitis are eligible for study participation.

Prior antibiotic/antifungal use exclusion

26. The participant has received treatment with other systemic antimicrobials or systemic antifungals within 1 week before study entry.

Concomitant medication use exclusion

27. The participant plans to use any of the prohibited medications or nondrug therapies from the Baseline Visit through 7 days after the first dose of study intervention as detailed in Section 6.9.

Prior/concurrent clinical study experience

28. The participant has been previously enrolled in this study or has previously been treated with gepotidacin.

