6.9.2. Prohibited medications and nondrug therapies

At the time of enrollment and/or during the study from the Baseline Visit through 7 days after the first dose of study intervention, the participant is prohibited from use of the following medications and nondrug therapies:

- An investigational product within 30 days or 5 half-lives, whichever is longer, of the Baseline Visit.
- Treatment with other systemic antimicrobials (e.g., oral ciprofloxacin, amoxicillin/clavulanate, cephalixin, or doxycycline) or systemic antifungals (e.g., oral fluconazole, itraconazole, or terbinafine) within 1 week before study entry. Treatment with systemic fluconazole or other systemic antifungals per local standard of care is only allowed 7 days after the first dose of study intervention.
- Immunosuppressive therapy, including corticosteroid therapy (>40 mg/day prednisolone or equivalent for >1 week, ≥ 20 mg/day prednisolone or equivalent for >2 weeks, or prednisolone or equivalent ≥ 10 mg/day for >6 weeks).
- QT-prolonging drugs or drugs with known TdP risk, per the www.crediblemeds.org “Known Risk of TdP” category, at the time of their Baseline Visit, which cannot be safely discontinued from the Baseline Visit through 7 days after the first dose of study intervention. Details regarding website access and additional guidance are provided in Appendix Section 10.4. Of note, ondansetron is not allowed from the Baseline Visit through 7 days after the first dose of study intervention due to its known TdP risk. Alternative antiemetics that are permitted per investigator discretion are listed in Appendix Section 10.4.

Note: Crediblemeds.org categorizes drugs into 4 categories. The only category for exclusion in this study is the “Known Risk of TdP” category; participants taking drugs that meet criteria of other categories are NOT excluded from participation.

- Strong CYP3A4 inhibitors (a list of strong CYP3A4 inhibitors is provided in Appendix Section 10.4).
- St John's wort or other strong CYP3A4 inducers are not permitted from 14 days before study entry through 7 days after the first dose of study intervention (a list is provided in Appendix Section 10.4).

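### A woman on a 'Known Risk of TdP' drug who can safely stop it at the Baseline Visit may receive gepotidacin that same day, although the risk table says such women are excluded

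*Protocol*

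**What the plan says.** Protocol Section 2.3.1, under cardiovascular effects, gives this mitigation: "Participants taking medications known to increase QT or potent CYP3A4 inhibitors will be excluded". It attaches no condition and refers to Section 6.9.2.

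The operative rules are in Section 5.2 and Section 6.9.2. Criterion 20 covers a woman who at Baseline is taking a drug in the CredibleMeds 'Known Risk of TdP' category "which cannot be safely discontinued from the Baseline Visit (Day 1) through 7 days after the first dose of study intervention". Section 6.9.2 repeats the condition: "which cannot be safely discontinued from the Baseline Visit through 7 days after the first dose of study intervention". It also limits the rule to that one category: "participants taking drugs that meet criteria of other categories are NOT excluded from participation". Its named example, ondansetron, is barred only from Baseline forward: "ondansetron is not allowed from the Baseline Visit through 7 days after the first dose of study intervention".

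The first gepotidacin dose is taken on site at Visit 1 (Schedule of Activities; Section 8). Triplicate ECGs are done before that dose, and criterion 21 excludes a mean QTc above 450 msec, or above 480 msec with bundle-branch block. Sections 7.1.2 and 8.3.3 require no ECG after Baseline, and SAP Section 4.1.2 agrees. Section 2.3.3 bases the benefit-risk conclusion on the safeguards: "Taking into account the measures taken to minimize risk to participants participating in this study".

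**The concern.** The risk table and the eligibility rule describe different populations. Someone reading 2.3.1, such as an ethics committee member, would conclude that a woman on a QT-increasing drug does not receive gepotidacin. A site following criterion 20 exactly may enrol her if she can safely stop at that visit, and dose her within the same visit.

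Stopping a drug at the visit does not remove it from the body. Section 2.3.1 reports concentration-dependent QT prolongation with gepotidacin. What is at stake is therefore an avoidable overlap of two QT-active drugs that the protocol presents as prevented and that no scheduled assessment would detect. No efficacy estimate is affected.

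**Working it through.** No sample-size or power figure is involved. The check compares the texts, follows one participant through the rules, and then sizes the effect with the figures the protocol gives.

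**1. The rules side by side**

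| Place | Who is excluded at Baseline | Condition |
|---|---|---|
| 2.3.1 | Users of QT-increasing drugs | None |
| Criterion 20 | Users of 'Known Risk of TdP' drugs | Only if the drug cannot be safely stopped |
| 6.9.2 | Same category | Same condition |
| Criterion 20, second half | Users of strong CYP3A4 or P-gp inhibitors | None |

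Criterion 20 and 6.9.2 agree with each other. Section 2.3.1 is wider than both in two respects: it omits the condition, and its wording is not limited to one CredibleMeds category.

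**2. One participant followed through**

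- She took a 'Known Risk of TdP' drug that morning, and the investigator judges that she can safely stop. Criterion 20 does not exclude her.
- Criterion 27 and the 6.9.2 ban bar further use through 7 days after the first dose. Neither deals with drug already absorbed.
- Her predose triplicate ECG is within the limit. It may well reflect the other drug, but it cannot show the combined effect because gepotidacin has not yet been given.
- She takes dose 1 at the visit. Scheduled ECGs across the 10 doses after that: 0.
- The planned contacts that follow are telephone calls. At Visits 2 to 5 the caller is the coordination center, which does not ask directly about adverse events. An ECG during dosing would need an unscheduled visit or the investigator's initiative.

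**3. Size**

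Inputs: the gepotidacin QTcF effect in the thorough QTc study (Section 2.3.1, infusions of 1000 and 1800 mg), given as "of 12 to 22 msec. The QT prolongation evolved during the infusion"; the entry limits of 450 and 480 msec (criterion 21); the matching stopping values of 500 and 530 msec and the change limit of 60 msec (Section 7.1.2).

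Assumptions: the effects add, the infusion figures apply to 1500 mg by mouth, and the other drug's share does not change after the predose ECG.

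- Without bundle-branch block: 450 + 12 = 462 and 450 + 22 = 472 msec. Distance to 500: 38 and 28 msec.
- With bundle-branch block: 480 + 12 = 492 and 480 + 22 = 502 msec. Distance to 530: 38 and 28 msec.
- Change from Baseline: 12 to 22 msec, which is 48 to 38 msec under the 60 msec limit.

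A woman starting exactly at the entry limit therefore stays below every stopping value under these assumptions. The third assumption is the weakest, since a tablet swallowed shortly before the ECG could still be absorbing. The documents report no combined effect.

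**The case against.** The case for leaving the text alone has real weight. Section 2.3.1 is a one-line summary that defers to 6.9.2, and the operative texts agree, so no site would be confused about whom to enrol. The rule requires that stopping be safe, which is a clinical judgment. The predose triplicate ECG is a direct check on each woman. Criteria 15 to 19 and 22 remove other high-risk women. Section 2.3.1 says the effect reversed quickly after infusion and that no medically significant QTc values were seen in Phase 1 and 2. All of this stands and limits the risk. None of it makes the statement in 2.3.1 true, and none of it measures the QTc after the first dose.

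A reader might infer three stronger points that the documents do not support.

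- *That these drugs are singled out by having no washout.* The protocol does set intervals for some classes; for example, "strong CYP3A4 inducers are not permitted from 14 days before study entry through 7 days after the first dose of study intervention". But strong CYP3A4 and P-gp inhibitors, in the same criterion, have no look-back either, and neither do NSAIDs or phenazopyridine. What is particular to 'Known Risk of TdP' drugs within criterion 20 is the exemption for women who can stop at the visit.
- *That participants would reach the QTc stopping values.* The arithmetic above does not show this.
- *That the time of last intake cannot be recorded without a new eCRF field.* Protocol Section 6.9 lists dates only, but SAP Section 6.3.3.1 uses time to classify medication taken on the first dose date, and SAP Section 6.3.8 imputes missing medication times. The SAP thus expects times to be available.

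**Conclusion.** The inconsistency is real and bears on safety wording and eligibility. Under criterion 20 and 6.9.2, a woman judged able to stop a 'Known Risk of TdP' drug safely at Baseline can receive gepotidacin at that visit with the other drug still present and with no ECG scheduled afterwards. Section 2.3.1 tells the reader that such women are excluded.

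The size is modest. On the stated assumptions, QTc remains 28 to 38 msec below the stopping values even from the entry limit. The number of women affected is not given and is likely to be small in a study of about 90. The change is worth making because it is cheap and makes the stated mitigation true, not because harm has been shown to be likely.

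**What to change.** 1. In criterion 20 and Section 6.9.2, delete the condition about not being able to discontinue safely. Any woman taking a 'Known Risk of TdP' drug at the Baseline Visit is then excluded, as criterion 20 already does for strong CYP3A4 and P-gp inhibitors.
2. Keep the ban on use from the Baseline Visit through 7 days after the first dose, and check that the shortened 6.9.2 bullet still says so.
3. In Section 2.3.1, replace the general reference to QT-increasing medication with the 'Known Risk of TdP' category. Appendix 10.4, which already calls such drugs exclusionary, then needs no change.

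The cost is wording in three places and a few current users becoming ineligible. Endpoints, analyses and data collection are unchanged.

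A look-back interval for women who stopped shortly before Baseline is optional and for the sponsor to decide. It would close the remaining gap for recent users, including a woman who fails screening, stops the drug and returns under the single rescreen that Section 5.4 allows. It has a price. With 5 half-lives, for example, the break-even half-life against the under-96-hour symptom window in criterion 2 is 96 / 5 = 19.2 h. A woman who stopped a longer-lived drug at symptom onset could not clear the interval in time.
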